#### Table 3-1: HeartLogic State

The CRT-D or ICD device, along with its associated leads, constitutes the implantable portion of the system. The external portion of the system includes the commercially available LATITUDE NXT 5.0 System (or future versions) and the Model 3120 Programmer Recorder Monitor (or future versions). The external portion of the system allows interrogation and programming of the PG, as well as access to the PG's diagnostic features.

Communication between the internal and external portions of the system is conducted through a handheld wand and/or wireless telemetry. Data are then transmitted to the clinician care team. The complete LATITUDE NXT 5.0 system is shown in Figure 3-1. Data will automatically be uploaded and transmitted to the clinician for review on the scheduled interval. When the HeartLogic alert threshold is met or exceeded, a yellow alert is generated which triggers the health care professional to review the data and take appropriate action.

Boston Scientific has performed safety risk management activities, design verification and design validation testing to demonstrate that devices with the HeartLogic feature function

safely and effectively per the design intent. The products conform to user needs and intended use, all system-level requirements have been tested with no uncorrected failures, and the risk is acceptable for normal product use in accordance with product labeling.

Figure 3-1: LATITUDE NXT 5.0 System

## 4 Study Objectives

There are two objectives of the MANAGE-HF multi-phase study :

- Phase I: To evaluate and optimize HeartLogic clinical integration and alert management process.
- Phase II: To evaluate HeartLogic in regards to patient outcomes of death and heart failure hospitalizations. Additionally, Phase II will fulfill regulatory requirements of post-approval study for HeartLogic.

Phase II of the MANAGE-HF trial will begin following completion of Phase I. Subjects enrolled in Phase I will be ineligible to enroll in Phase II.

## 5 Study Endpoints

The primary endpoint will assess the composite of all-cause mortality and heart failure hospitalizations collected in Phase II of the trial, comparing HeartLogic Alerts ON vs. Alerts OFF.

The following secondary endpoints will be evaluated using data collected during Phase II, comparing the HeartLogic Alerts ON vs. Alerts OFF:

• Freedom from all-cause mortality

- Freedom from heart failure hospitalizations (time to first event)
- Change in NYHA classification
- Change in Quality of Life
- Change in NT-proBNP
- Change in Medication Status

All randomized subjects in Phase II will be eligible for inclusion in the analyses of all study endpoints. No data from Phase I will be included in the analysis for the primary or secondary endpoints.

## 6 Study Design

MANAGE-HF is a multi-center, global, prospective, open label, multi-phase trial. Phase I will be non-randomized and a single arm. Phase II will be randomized in a 1:1 allocation to HeartLogic Alerts ON vs. Alerts OFF. Phase II will begin after the primary objective of Phase I – to evaluate and optimize HeartLogic clinical integration and the alert management process – has been fulfilled. Boston Scientific will communicate to sites the authorization to initiate enrollment into Phase II.

Eligible subjects in Phase I and Phase II will already be implanted with a device that contains HeartLogic, and must meet the inclusion and exclusion criteria as described in Sections 7.2 and 7.3. Subjects in Phase I are ineligible to be enrolled in Phase II.

The follow-up schedules are identical for all subjects in Phases I and II. Only the point of study exit differs between the phases. Follow-up for subjects in each phase are shown in the table below. Additional visits will occur in response to HeartLogic alerts.

Window	Phase I	Phase II			
After device implant	Х	Х			
At least 45 days of heart failure	Х	Х			
sensor data collection.					
At most 4 months from					
enrollment.					
$180 \pm 30$ days from baseline	$X^1$	$X^2$			
$545 \pm 30$ days from baseline					
$910 \pm 30$ days from baseline					
$1275 \pm 30$ days from baseline					
$1640 \pm 30$ days from baseline					
$365 \pm 30$ days from baseline	$X^1$	$X^2$			
$730 \pm 30$ days from baseline					
$1095 \pm 30$ days from baseline					
$1460 \pm 30$ days from baseline					
$1825 \pm 30$ days from baseline					
	After Phase I	After necessary			
	subjects complete	number of primary			
	$12 \text{ month visit}^3$	endpoint events has			
		been accrued			
1. Follow-ups continue for Phase I subjects through the end of Phase I					
2. Follow-ups continue for Phase II subjects through the end of Phase II					
	WindowAfter device implantAt least 45 days of heart failuresensor data collection.At most 4 months fromenrollment. $180 \pm 30$ days from baseline $545 \pm 30$ days from baseline $910 \pm 30$ days from baseline $1275 \pm 30$ days from baseline $1640 \pm 30$ days from baseline $365 \pm 30$ days from baseline $730 \pm 30$ days from baseline $1095 \pm 30$ days from baseline $1460 \pm 30$ days from baseline $1825 \pm 30$ days from baseline $1460 \pm 30$ days from baseline $1825 \pm 30$ days from baseline	WindowPhase IAfter device implantXAt least 45 days of heart failureXAt least 45 days of heart failureXsensor data collection.XAt most 4 months fromImage: Collection of the sensor data collection.At most 4 months fromImage: Collection of the sensor data collection.At most 4 months fromImage: Collection of the sensor data collection.At most 4 months fromImage: Collection of the sensor data collection.At most 4 months fromImage: Collection of the sensor data collection.At most 4 months fromImage: Collection of the sensor data collection.At most 4 months fromImage: Collection of the sensor data collection.At most 4 months fromImage: Collection of the sensor data collection.At most 4 months fromImage: Collection of the sensor data collection.At most 4 months fromImage: Collection of the sensor data collection.180 ± 30 days from baselineImage: Collection of the sensor data collection.1095 ± 30 days from baselineImage: Collection of the sensor data collection.1460 ± 30 days from baselineImage: Collection of the sensor data collection.1825 ± 30 days from baselineImage: Collection of the sensor data collection.190 continue for Phase I subjects through the end of Physe continue for Phase II subjects through the end of Physe continue for Phase II subjects through the end of Physe.			

#### Table 6-1: Scheduled Visits

3. Phase I may complete early upon recommendation from Steering Committee

After a minimum of 45 days of heart failure sensor data collection, all subjects (Phases I and II) will be evaluated at a baseline visit and will be followed annually for in-clinic visits. In addition, a 6 month phone call for all subjects will be placed in between annual visits. Subjects in Phases I and II will continue to be seen until the study phase is completed. Phase I ends when the final subject completes the 12 month follow-up visit, or upon recommendation from the Steering Committee. Phase II ends when the necessary number of primary endpoint events has been accrued. A detailed flow-chart of the study visits can be found in Section 9.

#### 6.1 Scale and Duration

The study will enroll up to a total of 2700 subjects across two study phases. Up to 200 subjects will be enrolled in Phase I in order to build critical knowledge about the clinical integration of HeartLogic and the alert management process. A minimum of 50% of the subjects in Phase I will come from US sites. Phase I will be concluded upon completion of the last Phase I subject's 12 month follow-up, or upon recommendation from the Steering Committee that the study should progress to Phase II. Subjects in Phase I will be ineligible to enroll in Phase II.

Up to 2500 subjects will be enrolled in Phase II to sufficiently power the primary endpoint in Phase II. A minimum of 50% of the subjects in Phase II will come from US sites. Follow-up for Phase II will continue until a pre-specified stopping boundary has been achieved or the necessary number of primary endpoint events has been accrued. Details of the pre-specified Primary Endpoint are defined in Section 10.1 and in a separate Statistical Analysis Plan. Phase I events will not count toward the primary endpoint of the study.

Figure 6-1 illustrates the study flow of both phases of the MANAGE-HF trial. Enrollment durations of Phases I and II are expected to last 15 and 24 months, respectively. A gap in time between completion of Phase I enrollments and initiation of Phase II enrollments is anticipated as Phase I patients may be followed until the final patient finishes the 12 month visit.

Figure 6-1: MANAGE-HF Study Design

#### 6.2 Treatment Assignment

The MANAGE-HF post-approval study is a multi-phase study. Phase I is single arm and open label; all enrolled Phase I subjects will be actively managed with HeartLogic alerts. Subjects in Phase I will be ineligible to be enrolled in Phase II.

Phase II is randomized, controlled, two arm and open label. Phase II subjects will be randomized to HeartLogic Index and Alerts ON or HeartLogic Index and Alerts OFF using a 1:1 allocation. Randomization will be stratified by investigational center and device type (ICD or CRT-D).

The devices are commercially approved for use in patients indicated for an ICD or CRT-D. However, there are specific study criteria that are identical for both phases of MANAGE-HF that must be met to be eligible for enrollment (Section 7).

6.2.1 Treatment and Control

Phase I:

- All subjects in Phase I will be implanted with ICD or CRT-D devices that have the HeartLogic feature.
- HeartLogic Index and Alerts will be ON for all subjects enrolled in Phase I starting at the baseline visit.
- There will be no control subjects in Phase I.
- Subjects enrolled in Phase I will be ineligible for Phase II.
- Phase I data does not count toward Phase II endpoints.

Phase II:

- All subjects in Phase II will be implanted with ICD or CRT-D devices that have the HeartLogic feature.
- Subjects enrolled in Phase II will be randomized to HeartLogic Alerts ON (treatment) or HeartLogic Alerts OFF (control).
- Phase II subjects randomized to the treatment arm will be actively managed with the HeartLogic Alerts ON and the subjects randomized to the control arm will be managed with HeartLogic Alerts OFF.
- Randomized subjects in Phase II are eligible to contribute data to all endpoint analyses.

#### 6.3 Justification for the Study Design

The multi-phase nature of MANAGE-HF is required to evaluate the multiple objectives of the trial. The use of a single arm in Phase I was chosen as the most appropriate and efficient

design to evaluate and optimize HeartLogic clinical integration and alert management process. Learnings from Phase I will be incorporated into Phase II and reflected in a separate statistical analysis plan that will be approved by Boston Scientific and the FDA. The use of a randomized controlled design in Phase II was chosen to minimize bias in the findings, and is to the gold-standard to demonstrate a true treatment effect.

#### 6.4 Transition from Phase I to Phase II

It is anticipated that 200 subjects followed for a minimum of 12 months is required to fulfill the objectives of Phase I. After the final Phase I subject has completed their 12 month visit, or upon recommendation from the Steering Committee, Boston Scientific will notify sites to begin exiting Phase I subjects from the study.

Boston Scientific will notify sites of Phase II initiation, at which time all approved-to-enroll sites may begin enrolling Phase II subjects. Phase I subjects are ineligible to participate in Phase II. The request for randomization of subjects will occur at the baseline visit for Phase II subjects.

## 7 Subject Selection

## 7.1 Study Population and Eligibility

Eligibility for study enrollment is determined by specific inclusion and exclusion criteria as described in Sections 7.2 and 7.3.

#### 7.2 Inclusion Criteria

Inclusion criteria are identical for Phases I and II. Subjects who meet all of the following criteria (see Table 7-1) may be given consideration for inclusion in this clinical investigation, provided no exclusion criterion (see Section 7.3) is met.

CI1	Subject is age 18 or above, or of legal age to give informed consent					
CI2	Implanted with an CRT-D or ICD device that has HeartLogic					
CI3	Current symptomatic heart failure or NYHA Class II or III at the time of enrollment					
CI4	Remotely monitored by LATITUDE NXT 5.0 (or future versions)					
CI5	Willing and capable of participating in all study visits and complying with medication/treatment requirements associated with this clinical study at an approved clinical study center.					
CI6	
 
Meet at least one of the three following conditions:
 
At least one documented hospitalization with a primary diagnosis of worsening for heart failure during the 12 months prior to enrollment; or
 
Unscheduled outpatient visit with IV diuretic therapy for acute worsening of HF during 90 days prior to enrollment; or
 
NT-proBNP greater than 600 pg/mL or BNP greater than 150 pg/mL at any time during 90 days prior to enrollment
 
					

#### 7.3 Exclusion Criteria

All exclusion criteria apply to subjects in Phases I and II, except for criteria 10 and 11, which are applicable to Phase II subjects only. Subjects who meet any one of the following criteria (see Table 7-2) will be excluded from this clinical study.

14010 /					
CE1	The subject is unable to sign or refuses to sign the patient informed consent				
CE2	Symptomatic heart failure at rest or NYHA Class IV at the time of enrollment				
CE3	The subject is implanted with unipolar RA or RV leads				
CE4	Subject has received or is scheduled to receive a heart transplant or ventricular assist				
	device within the next 6 months				
CE5	Subject is pregnant or planning to become pregnant during the study				
CE6	Subject is enrolled in any other concurrent study (without prior written approval				
	from BSC, excluding registries)				
CE7	GFR <25 mL/min who are non-responsive to diuretic therapy or are on chronic renal				
	dialysis				
CE8	Regularly scheduled IV heart failure therapy (e.g. inotropes or diuretics)				
CE9	A life expectancy of less than 12 months per clinician discretion				
CE10	APPLICABLE TO PHASE II ONLY: Subject enrolled in Phase I of MANAGE-HF				
CE11	APPLICABLE TO PHASE II ONLY: Subject has been managed with HeartLogic				
	Alerts ON at anytime within the past 6 months.				
Abbreviations: RA=right atrial; RV=right ventricle					

#### Table 7-2: Exclusion Criteria

## 8 Subject Accountability

#### 8.1 Point of Enrollment

All details in this section apply to subjects in Phases I and II.

Subjects are considered enrolled at the point when they sign and date the informed consent form. Confirmation that inclusion and exclusion criteria are met must take place prior to consent. The consent may be obtained at any point in time following the implantation of the device, but not before.

#### 8.2 Point of Study Exit

#### 8.2.1 Study Completion

All details described in this section apply to subjects in Phases I and II.

Phase I:

After the final Phase I subject has completed their 12 month visit, or upon recommendation from the Steering Committee, Boston Scientific will notify sites to begin exiting Phase I subjects from the study. Boston Scientific will communicate to the sites the strategy for exiting subjects at the end of the study.

Phase II:

After the necessary number of primary endpoint events has been accrued, Boston Scientific will notify sites to begin exiting Phase II subjects from the study.

8.2.2 Withdrawal

All details described in this section apply to subjects in Phases I and II.

All subjects enrolled in the clinical study (including those withdrawn from the clinical study or lost to follow-up) shall be accounted for and documented. If a subject withdraws from the clinical investigation, the reason(s) shall be reported. If such withdrawal is due to problems related to investigational device safety or performance, the investigator shall ask for the subject's permission to follow his/her status/condition outside of the clinical study.

A subject who becomes inactive in the study as defined by clinician recommendation, subject choice, has their device explanted, or is lost to follow-up will be classified as "Withdrawal". All applicable case report forms up to the point of withdrawal and a "Subject Status" form must be completed. Investigators who have "lost-to-follow-up" subjects should have at least three documented attempts to contact them prior to completion of the "Patient Status" form.

After a subject has been withdrawn from the study or after a subject has withdrawn his/her consent, for whatever reason, additional data may no longer be collected after the point of withdrawal, and HeartLogic alerts may be turned OFF. All open adverse events should be closed or documented as chronic. Data collected up to the point of subject withdrawal may be used for analysis. Boston Scientific will not actively collect any information on subjects who have been withdrawn from the study after the withdrawal date. However, all post-withdrawal adverse events of which Boston Scientific is notified will be recorded in the patient file.

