# 9.3.5 End of Study

Details apply to all subjects in Phases I and II.

End of study for a subject occurs when the subject dies, withdraws, completes study/phase participation or is withdrawn by the investigator. The clinician must document reason for study exit and date of study exit. HeartLogic Alerts may be configured at the discretion of the clinician at the end of the study.

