10.2.1 Secondary Endpoint 1: Freedom from all-cause mortality

Survival (freedom from all-cause mortality) between the randomized groups will be assessed, including all deaths occurring during Phase II of the trial.

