#### 10.3.2 Analysis Sets

All primary and secondary endpoint analyses will be performed following intention-to-treat (ITT) methodology, in which each subject is analyzed per their intended (i.e., randomized) treatment assignment. An as-treated analysis will be performed as well, in which subjects would be analyzed per the treatment received and may be time-varying to accommodate cross-overs. A per-protocol analysis will also be performed.

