#### 18.1 Reportable Events by Investigational site to Boston Scientific

It is the responsibility of the investigator to assess and report to BSC the following adverse events:

- All Serious Adverse Events ٠
- All cardiac related Adverse Events, including new onset of cardiac events, or worsening in severity or frequency of pre-existing cardiac condition(s)
- All Device Deficiencies •
- Unanticipated Adverse Device Effects/Unanticipated Serious Adverse Device Effects
- Protocol required procedures that result in an adverse event ٠
- Adverse Device Effects including Serious Adverse Device Effects •

HeartLogic Alerts are not considered adverse events, but may indicate the presence of an adverse event. If the criteria of a reportable adverse event have been fulfilled, an adverse event must be reported.

When possible, the medical diagnosis should be reported as the Event Term instead of individual symptoms. Multiple symptoms related to a single medical diagnosis should be reported within one (1) adverse event (i.e. shortness of breath and edema are related to a diagnosis of 'worsening heart failure').

If it is unclear whether or not an event fits one of the above categories, or if the event cannot be isolated from the device or procedure, it should be submitted as an adverse event and/or device deficiency.

Any AE experienced by the study subject after informed consent (as defined in study subject classification section) must be recorded in the eCRF. All AEs must be reported until the study phase is completed for each subject.

Underlying diseases are not reported as AEs unless there is an increase in severity of frequency during the course of the investigation. Death should not be recorded as an AE, but should only be reflected as an outcome of one (1) specific SAE (see Table 18-1 for AE definitions).

Refer to Section 17.3 for the known risks associated with the study device(s).

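### Section 8.2.2 ends outcome collection at device explant or clinician-recommended exit even where consent stands, so Phase II death and HF hospitalization data will be incomplete

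*Combined protocol and SAP*

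**What the plan says.** Section 8.2.2 applies to both phases. It defines the class broadly: "A subject who becomes inactive in the study as defined by clinician recommendation, subject choice, has their device explanted, or is lost to follow-up" is recorded as a withdrawal. Collection stops once a subject has been withdrawn or has withdrawn consent. These are listed as alternatives, so intact consent does not preserve follow-up. The consequence is that "additional data may no longer be collected after the point of withdrawal, and HeartLogic alerts may be turned OFF". The sponsor's position is firmer still: "Boston Scientific will not actively collect any information on subjects who have been withdrawn from the study after the withdrawal date".

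The section has two exceptions:

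- A subject leaving because of device safety or performance problems is asked for permission to be followed, but outside the study.
- "all post-withdrawal adverse events of which Boston Scientific is notified will be recorded in the patient file". No route from that file to adjudication or to the endpoint analysis is given.

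Section 9.3.5 closes participation at the same point: "End of study for a subject occurs when the subject dies, withdraws, completes study/phase participation or is withdrawn by the investigator".

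Other sections need more than this:

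- Section 10.3.2: "All primary and secondary endpoint analyses will be performed following intention-to-treat (ITT) methodology".
- Section 10.2.1 compares survival "including all deaths occurring during Phase II of the trial".
- Section 5 makes all randomized Phase II subjects eligible for every endpoint analysis.
- Section 18.1: "All AEs must be reported until the study phase is completed for each subject".

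**The concern.** Subjects who are explanted, or whose clinician recommends exit, can still be contacted and have not withdrawn consent. Dropping them at that point censors them on an event that may be related to prognosis or to arm.

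Two mechanisms could move the hazard ratio:

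1. **The benefit ends at exit.** Alerts may be switched off after withdrawal, and an explanted device cannot alert. Censoring there leaves out person-time in which the ON arm no longer benefits. The estimate is then more favourable than under full follow-up, even if both arms exit at the same rate.
2. **Exit depends on arm and prognosis.** Phase II is open label (Section 6.2), alerts and the required response exist only in the ON arm (Section 9.4), and crossover is not allowed (Section 9.8). A link between arm and exit is plausible, but the documents contain no evidence of one. The resulting bias could favour either arm.

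The trial is also event-driven (Section 10.1.2), so uncollected events lengthen it.

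**Working it through.** **Textual check.** Sections 8.2.2 and 9.3.5 end collection when a subject is withdrawn. Section 10.2.1 needs deaths up to the end of Phase II. No section provides vital-status or hospitalization follow-up for a withdrawn subject who still consents. Neither exception in 8.2.2 gives systematic ascertainment.

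**Size.** The plan has no figure to reproduce. Hazard ratio, power, event rate, event target and dropout are left to a separate SAP (Sections 10.1.2 and 10.1.3). Every input below is an assumption except 1:1 allocation (Section 6), 24-month accrual (Section 6.1) and one-sided 2.5% (Section 10.3.4).

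- Endpoint: time to first death or HF hospitalization.
- Hazard before exit, λ: 0.20 per year control; 0.20 × 0.80 = 0.16 ON.
- Closure at 4 years, so administrative follow-up is uniform on 2 to 4 years: G(t) = 1 up to year 2, then (4 − t)/2.
- Exit rate w per year: recoverable exits only (explant, clinician recommendation).
- Hazard after exit, μ: m × own-arm hazard if the benefit continues; m × 0.20 in both arms if it stops; m = 1, 2, 3.

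For each arm:

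- Event-free and in study: P(t) = exp(−(λ + w)t).
- Event-free after exit: E(t) = w[exp(−μt) − exp(−(λ + w)t)]/(λ + w − μ).
- Censored analysis: at risk Y = G·P, event density f = G·P·λ.
- Full follow-up: Y = G(P + E), f = G(P·λ + E·μ).

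The large-sample Cox hazard ratio θ solves ∫[f_ON − (f_ON + f_OFF)·θY_ON/(θY_ON + Y_OFF)]dt = 0.

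The censored θ is 0.8000 in every scenario. Full-follow-up θ is:

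| Exits per year, ON vs control | Benefit continues, m = 1 / 2 / 3 | Benefit stops, m = 1 / 2 / 3 |
|---|---|---|
| 1% vs 0.6% | 0.8000 / 0.8040 / 0.8071 | 0.8027 / 0.8077 / 0.8112 |
| 1.5% vs 0.5% | 0.8000 / 0.8095 / 0.8168 | 0.8040 / 0.8152 / 0.8229 |
| 1% vs 1% | 0.8000 / 0.8003 / 0.8010 | 0.8027 / 0.8041 / 0.8051 |
| 0.6% vs 1% | 0.8000 / 0.7966 / 0.7945 | 0.8016 / 0.7988 / 0.7970 |
| 0.5% vs 1.5% | 0.8000 / 0.7912 / 0.7855 | 0.8013 / 0.7931 / 0.7875 |

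- Largest gap: 0.8229 − 0.8000 = 0.023. With control hazard 0.10 or 0.30 per year it is 0.029 or 0.019.
- First events missed in the top three rows: 1.1% to 3.1%.
- Sampling error at an assumed 700 events: SE(log HR) = 2/√700 = 0.0756; × 0.80 = 0.060. Then 0.023/0.060 = 0.38.
- Time to 700 events with N = 2000, benefit stopping: at 1% vs 0.6%, 3.42 vs 3.45 years (m = 1) and 3.39 vs 3.45 (m = 3); at equal 1%, 3.43 vs 3.47 and 3.38 vs 3.46. The delay is 12 × 0.03 = 0.4 to 12 × 0.08 = 1.0 months.

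**Stress case under the null.** Suppose the true HR is 1 and exits fall just before 2% of control events and 5% of ON events. The apparent HR is 0.95/0.98 = 0.969. The one-sided error, Φ(−√(d/4)·ln 0.969 − 1.96), is 0.050 at d = 400 events and 0.064 at d = 800. With equal losses it stays at 0.025.

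**Upper bound, only if every exit were recoverable.** With m = 3 and the benefit stopping, 5% vs 3% gives 0.8521 and 6% vs 2% gives 0.8865. Consent withdrawals and most losses to follow-up cannot be recovered, so these figures mark a limit and are not an expectation.

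**The case against.** The strongest reply is about size. The likely effect is small against sampling error, and the largest base-case gap needs three assumptions together: a threefold exit ratio, tripled hazard after exit, and benefit stopping at exit. With equal 1% exits the gap is at most 0.005. With the unequal arms reversed it runs from +0.002 to −0.0145, so in most of those cells censoring at exit is conservative. All of this stands and limits the priority of the point.

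Second, Section 10.3.2 defines intention-to-treat by how subjects are grouped, and censoring at withdrawal is compatible with that wording. This is fair. The firmer conflict is with Section 10.2.1, which counts all Phase II deaths. Sections 10.2.2 and 10.2.3 limit the hospitalization endpoints to observed data.

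Third, Section 18.1 can be read with Section 9.3.5 so that adverse event reporting also stops at withdrawal. That reading is possible. It would leave 18.1 no help in filling the gap, so a clarification is still needed.

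Fourth, the separate SAP may already contain censoring rules and sensitivity analyses. It may, but it cannot supply outcomes the protocol does not collect.

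Fifth, the number affected is unknown and may be small. This is true: the documents give no exit rate.

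**Conclusion.** The concern holds. As written, the protocol stops collecting endpoint events in randomized Phase II subjects who could still be followed, while Section 10.2.1 counts all deaths in that phase and Section 10.3.2 commits to intention-to-treat.

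Under the stated assumptions, 1.1% to 3.1% of first events would be missed, and the HR would typically shift by 0.00 to 0.02 on 0.80. That is under 0.4 of a standard error in the base case, in either direction. The gaps assume closure at 4 years, whereas 700 events arrive at about 3.4 years, so the comparison with the standard error is approximate.

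This should be fixed, but it does not threaten the trial. The case for acting is that the loss is avoidable at little cost and cannot be repaired at analysis. Confidence in the size is moderate because the exit and event rates are assumed.

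**What to change.** For Phase II:

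1. Amend Sections 8.2.2 and 9.3.5 so that explant or clinician-recommended exit is recorded as a status change and does not end outcome follow-up. Only withdrawal of consent should end data collection.
2. Keep these subjects under follow-up for death and hospitalization to the common Phase II cut-off. Use the existing six-monthly rhythm (calls in Section 9.3.3.1 alternating with visits in 9.3.3.2), reduced to outcome ascertainment where device procedures no longer apply. Send events to the Clinical Events Committee (Section 20.3) and analyze as randomized.
3. For subjects lost after the three documented contact attempts, seek vital status at study close where consent and local law allow.
4. Reconcile Section 18.1 with 8.2.2, and say what happens to outcome follow-up at a terminated site (Section 21.4).
5. If the separate SAP does not already do so, tabulate exits by arm and reason, and add one sensitivity analysis for informative censoring.

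The cost is protocol and Phase II consent wording, plus some phone contacts, vital-status checks and adjudications for the subjects who exit. No additional patients are needed. Phase II follows Phase I and has its own consent form (Sections 6.4 and 19). If it has not opened, the change can be made before anyone is randomized.
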